10.3. Analysis Sets

10.3.1. Efficacy Analysis Sets

10.3.1.1. Intent-to-Treat

The ITT population (also known as the full analysis set) is defined as all randomized patients who received at least 1 dose or part of a dose of double-blind study drug and have an evaluable primary endpoint. The endpoint is evaluable when the following 2 conditions are met:

- Availability of at least 1 measurement value for calculated LDL-C before first dose of study drug (ie, baseline).
- Availability of at least 1 measurement value for calculated LDL-C within 1 of the analysis windows up to week 16.

Patients in the ITT population will be analyzed according to the treatment group allocated by randomization (ie, as-randomized group).

10.3.1.2. Modified Intent-to-Treat

The modified intent-to-treat (mITT) population is defined as all randomized patients who took at least 1 dose or part of a dose of study drug and have an evaluable primary endpoint. The primary endpoint is considered as evaluable when both of the following conditions are met:

- Availability of at least 1 measurement value for calculated LDL-C value before first dose of study drug (ie, baseline).
- Availability of at least 1 calculated LDL-C value during the efficacy treatment period and within 1 of the analysis windows up to week 16. The group A (SC dose regimens) efficacy treatment period is defined as the time from the first study drug administration up to 14 days after the last double-blind study drug injection. The Group B (IV dose regimens) efficacy treatment period is defined as the time from the first study drug administration up to 35 days after the last double-blind study drug infusion, or up to the first dose of the open-label study drug, whichever is earlier.

Patients in the mITT population will be analyzed according to the treatment group allocated by randomization.

10.3.2. Safety Analysis Set

10.3.2.1. Double-Blind Safety Analysis Set

The double-blind safety analysis set (SAF) population considered for safety analyses will be the randomized patients who received at least 1 dose or part of a dose of study drug. Patients will be analyzed according to the treatment received (as-treated placebo or evinacumab).

In addition:

- Randomized patients, for whom it is unclear whether they took the study drug, will be included in the SAF as randomized.
- For patients receiving study drug from more than 1 treatment group during the trial, the treatment group allocation for as-treated analysis will be the one in which the patient was treated with the highest number of injections (Group A) or infusions (Group B).

Treatment compliance/administration and all clinical safety variables will be analyzed using the SAF.

10.3.2.2. Open-Label Safety Analysis Set

For Group B, the open-label SAF considered for safety analyses will be the randomized population who received at least 1 dose or part of a dose of open-label study drug.

10.3.3. Pharmacokinetic and Anti-drug Antibody Analysis Sets

The PK population includes all treated patients who received any study drug (safety population) and had at least 1 non-missing drug concentration result following the first dose of study drug.

The ADA population includes all treated patients who received any study drug (safety population) and had at least one non-missing ADA assay result following the first dose of study drug.

10.3.4. Pharmacodynamic Analysis Set

The PD population includes all treated patients who received any study drug (safety population) and had at least one non-missing ANGPTL3 value or other protocol defined PD marker (Section 8.2.5) following the first dose of study drug.

10.4. Statistical Methods

Unless otherwise noted, descriptive statistics for continuous variables will include the following information: the number of patients reflected in the calculation (n), mean, median, SD, minimum, and maximum. For categorical variables, frequencies and percentages will be displayed for each category.

10.4.1. Patient Disposition

The following data will be summarized:

- The total number of screened patients, defined as having met the inclusion criteria and signed the ICF.
- The total number of randomized patients, defined as all screened patients with a double-blind treatment kit number allocated and recorded in the IVRS database, regardless of whether the treatment kit was used.

For any patient randomized more than once, safety data from the first randomization will be included in the SAF, with safety data associated with the later randomization reported separately. Since this is expected to be a rare event, inclusion of efficacy data from the patient randomized more than once in the efficacy population will be decided on a case-by-case basis prior to the unblinding of treatment assignments and will be documented in the clinical study report.

- The total number of patients randomized, but not receiving study treatment
- The total number of patients randomized and receiving study treatment
- The total number of patients who completed the double-blind treatment period, defined for Group A as at least 15 weeks of study treatment exposure and week 16 visit performed; and defined for Group B as at least 20 weeks of study treatment exposure and week 24 visit performed
- The total number of Group B patients who completed week 16 visit, defined as at least 12 weeks of study treatment exposure and week 16 visit performed
- The total number of Group B patients who completed the open-label treatment period, defined as at least 44 weeks of open-label study treatment exposure and visit week 72 performed.
- The total number of patients who prematurely discontinued study treatment during the double-blind treatment period, and the reasons for discontinuation
- The total number of patients who prematurely discontinued study treatment during the open-label treatment period, and the reasons for discontinuation
- The total number of patients who did not complete the study follow-up period, defined as the last visit performed less than 23 weeks after the last study treatment administration. Patients who died during the study are excluded
- The total number of patients in each analysis set
- A listing of patients treated but not randomized, patients randomized but not treated, and patients randomized but not treated as randomized
- A listing of patients prematurely discontinued from treatment, along with reasons for discontinuation

10.4.2. Demography and Baseline Characteristics

For the double-blind treatment period, demographic and baseline characteristics will be summarized descriptively by treatment group in the ITT population. For the Group B open-label treatment period, demographic and baseline characteristics will be summarized descriptively by

treatment group assigned in the double-blind period, as well as for patient total, for patients in the open-label SAF.

10.4.3. Efficacy Analyses

10.4.3.1. Primary Efficacy Analysis

For the double-blind primary efficacy analysis, the percent change from baseline in calculated LDL-C at week 16, as defined in Section 4.2, will be analyzed in the ITT population using a mixed-effect model with repeated measures (MMRM) approach. All post-baseline data available within week 2 to week 16 analysis windows will be used and missing data are accounted for by the MMRM model. Each model will include the fixed categorical effects of treatment group (placebo and evinacumab dose regimens), randomization strata, time point (weeks 4, 8, 12, 16 for the Group B treatment groups; weeks 2, 4, 6, 8, 12, 16 for the Group A treatment groups), strata-by-time point interaction, and treatment-by-time point interaction, as well as the continuous fixed covariates of baseline LDL-C value and baseline value-by-time point interaction. Contrast and estimate statements will be used to assess the treatment effects (LS means with confidence intervals) and each dose regimen pairwise comparison to placebo (mean difference and p-values).

This model will be run separately for each route of administration (Group A or Group B, with Group B consisting of 3 dose regimens for the variability estimate) using an unstructured correlation matrix to model the within-patient errors. Parameters will be estimated using a restricted maximum likelihood method with the Newton-Raphson algorithm. Denominator degrees of freedom will be estimated using Satterthwaite's approximation.

The 4 primary treatment group comparisons will evaluate at week 16 each evinacumab dose regimen to the placebo group corresponding to the route of administration (IV or SC).

1. Evinacumab 15 mg/kg IV Q4W compared to Placebo IV
2. Evinacumab 450 mg SC QW compared to Placebo SC
3. Evinacumab 300 mg SC QW compared to Placebo SC
4. Evinacumab 300 mg SC Q2W compared to Placebo SC

The statistical testing of the 4 pairwise comparisons for the primary measure will be evaluated at a 2-sided significance level of 0.05 per pair wise comparison, adjusting for multiplicity through a hierarchical inferential approach.

Robustness of this statistical method will be assessed through sensitivity analyses detailed in the SAP, including the effects of missing data on the primary efficacy endpoint (pattern mixture modeling which will take into account the differing missing value patterns based on calculated LDL-C collected in the presence or absence of study treatment administration), and an on-treatment analysis of the primary endpoint (mITT patient population).

10.4.3.2. Secondary Efficacy Endpoint Analysis

For secondary efficacy endpoints (defined in Section 4.2) collected in the double-blind treatment period, descriptive summaries and analyses will be performed in the ITT population for each of the 5 pairwise treatment group comparisons, including the comparison of evinacumab 5 mg/kg IV Q4W patient treated group to the Placebo IV group.

For descriptive summaries, percent change, and when appropriate absolute change from baseline, in calculated LDL-C, total-C, HDL-C, TG, non-HDL-C, ApoB, ApoA-1, and Lp(a) will be provided at each time point. All measurements, scheduled or unscheduled, will be assigned to analysis windows defined in the SAP in order to provide an assessment for these time points. Laboratory assessments other than the ones provided by the central laboratory will be excluded. For TG, measurements on non-fasting patients will be excluded. The time profile of each parameter will be plotted by treatment group with the corresponding standard errors.

Multiple types of measurements are planned to be analyzed during differing time points in the trial, specifically continuous measurements expected to have a normal distribution (example: percent change in calculated LDL-C), continuous measurements expected to have a non-normal distribution (example: TG), and binary measurements (example: proportion of patients reaching LDL-C < 100mg/dL).

I. Continuous endpoints anticipated to have a normal distribution

Continuous secondary variables defined in Section 4.2 anticipated to have a normal distribution (ie, lipids other than TG and Lp[a]) will be analyzed separately for Group A and Group B using the same MMRM model as for the primary endpoint. Specifically, the model will contain fixed categorical effects of treatment group, randomization strata, planned time points up to the time point of interest, strata-by-time point interaction and treatment-by-time point interaction, as well as the continuous fixed covariates of corresponding baseline value and baseline value-by-time point interaction.

II. Continuous endpoints anticipated to have a non-normal distribution

Continuous secondary efficacy endpoints defined in Section 4.2 anticipated to have a non-normal distribution (ie, TG and Lp(a)), will be analyzed using a robust regression model (ie, ROBUSTREG SAS procedure with M-estimation option) with treatment group and randomization stratum as main effect and corresponding baseline value(s) as covariate. Missing values will be addressed using a multiple imputation approach, which will be described in the SAP. The variables in the multiple imputation model will at least include the same variables as used in the robust regression model. The treatment group combined means will be provided with respective standard error (SE) estimates. The combined mean difference between the treatment groups will be provided with the SE, 95% confidence interval and p-value.

III. Binary endpoints

Binary secondary efficacy endpoints defined in Section 4.2 will be analyzed using stratified logistic regression (using the strata option of the SAS logistic procedure) with treatment group and randomization stratum as main effect and corresponding baseline value(s) as covariate. Missing values will be addressed using a multiple imputation approach, which will be described in the SAP. The variables in the multiple imputation model will at least include the same variables as used in the logistic regression model. Treatment effects will be compared and the combined odds ratio estimate between the treatment groups, with their corresponding 95% confidence intervals and p-value will be provided.

In the data dependent case that the logistic regression method is not applicable (eg, the response rate is zero in one treatment arm and thus the maximum likelihood estimate may not exist), the LOCF (last observation carried forward) approach would be used for handling of missing values

and an exact conditional logistic regression would be performed to compare treatment effects. The LOCF imputation method will consist of using the last value obtained up to the week 16 time window to impute the missing week 16 value.

10.4.3.3. Dose-Response Analysis

Within each route of administration (Group A or Group B), a dose-response descriptive analysis is planned for the evinacumab dose regimens, with the placebo group in the role of the null dose, for patients in the ITT population. Summary tables will provide descriptive statistics (at least mean, median, SD, min/max) for percent change from baseline in LDL-C at each protocol planned visit in the double-blind period, by treatment group. Graphs will provide mean and standard error bars for percent change from baseline in calculated LDL-C at each protocol planned visit, by treatment group.

In addition to the analyses results for each evinacumab dose regimen comparison to placebo, the comparisons among the evinacumab dose regimens will be assessed in the ITT population for the percent change from baseline in calculated LDL-C at week 16. This analysis will employ the same statistical methodology as described for the primary comparisons, specifically the MMRM approach, for evaluating effects among the evinacumab dose regimens. P-values will be provided for descriptive purposes to aid in interpretation of the dose-response.

10.4.3.4. Subgroup Analysis

To assess the evinacumab treatment effect during the double-blind treatment period on the stratification variable HeFH (Yes/No), specifically the strata level containing patients diagnosed with HeFH (Yes), a subgroup analysis is planned for the change from baseline LDL-C in the ITT population for each route of administration (Group A or Group B). Specifically, the primary MMRM model used to assess the treatment group pairwise comparisons will have the additional variables of treatment-by-HeFH strata and treatment-by time point-by HeFH strata interaction terms. For each dose regimen versus placebo at week 16, the LS mean treatment group difference will be provided for the HeFH (Yes) strata level, along with the corresponding SE, 95% CI and p-value (p-value is provided for descriptive purposes only). The HeFH (Yes/No) stratification factor to be used for this subgroup analysis will be as recorded in the electronic data capture system.

In addition, evinacumab treatment effect will also be explored in patients with a baseline LDL-C ≥ 100 mg/dL or ≥ 130 mg/dL during the double-blind treatment period.

10.4.3.5. Multiplicity Considerations

To control the 5% overall type-I error for the 4 pairwise comparisons in the primary analysis, the overall study α level will be controlled by the use of a hierarchical inferential approach. Statistical significance of the first pairwise treatment comparison is required before drawing inferential conclusions about the second pairwise treatment comparison at the 0.05 alpha level. Inferential conclusions about successive pairwise treatment comparisons require statistical significance of the prior treatment comparison. The hierarchy testing sequence is the order of treatment comparisons as presented in Section 10.4.3.1. This fixed hierarchical approach will ensure a strong control of the overall type-I error rate at the 0.05 level for each evinacumab dose regimen comparison.

No further adjustments will be made for secondary efficacy endpoints collected during the double-blind treatment period, nor for the comparison of the evinacumab 5 mg/kg IV Q4W patient treated group to the Placebo IV group on any efficacy endpoint collected during the double-blind treatment period. P-values will be provided for descriptive purposes only.

10.4.4. Safety Analysis

In general, for the double-blind period, the summary of safety results for patients in the double-blind SAF population will be presented by route of administration (Group A or Group B), pooling the evinacumab dose regimens within each route of administration (Group A or Group B), with the intent to maximize efforts to identify potential safety signals. The treatment group data (individual evinacumab dose regimens and placebo) will also be presented with the intent to support the pooled dose regimens. No formal inferential testing will be performed. Summaries will be descriptive in nature.

For Group B, summaries of safety results for the open-label period will be presented for patients in the open-label SAF, by the total patients administered open-label study treatment (total), as well as by the patient subgroups of study treatment received in the double-blind treatment period (ie, evinacumab dose, placebo).

All safety analyses will use the following common rule:

- The baseline value is defined as the last available value before the first dose of study drug.

10.4.4.1. Adverse Events

Definitions

For safety variables, the following observation periods are defined:

- The pre-treatment period is defined as the day the ICF is signed to the day before the first dose of double-blind study drug.
- The double-blind TEAE period is defined for each route of administration from the day of the first dose of double-blind study treatment to the day of the last dose of double-blind study treatment + 168 days (24 weeks) (based on PK considerations, residual effect of study treatment might be observed until 24 weeks after the last dose of study drug) for those patients not proceeding into the open-label treatment period (ie, Group A patients and Group B patients who prematurely discontinue study treatment), or up to the day before the first dose of open-label study treatment administration for those patients proceeding into the open-label treatment period
- The open-label TEAE observation period is defined from the day of the first open-label study treatment administration to the day of the last open-label study treatment administration + 168 days (24 weeks).
- The post-treatment period is defined as the time from the day after the end of the respective TEAE periods to the last study visit.

Double-blind TEAEs are defined as those events that developed, worsened, or became serious during the double-blind TEAE period. Open-label TEAEs are defined as those events that developed, worsened, or became serious during the open-label TEAE period.

Analysis

All AEs reported in this study will be coded using the currently available version of the Medical Dictionary for Regulatory Activities (MedDRA[®]). Adverse event incidence tables will present data by system organ class (SOC) sorted alphabetically and preferred term (PT) sorted by decreasing frequency, and summarize the number (n) and percentage (%) of patients experiencing an AE. Multiple occurrences of the same event in the same patient will be counted only once in the tables. Data conventions for missing or partial AE dates will be addressed in the SAP. The denominator for computation of percentages is the respective SAF populations (ie, double-blind SAF or open-label SAF) within each treatment group.

Summaries of TEAEs incidences will include:

- All TEAEs (and patient listing)
- All treatment-emergent SAEs, including patient deaths (and patient listing)
- All TEAEs of interest, which will be defined by a PT or a prespecified grouping of terms
- TEAEs by severity (according to the grading scale outlined in Section 9.5.1), depicting the worse TEAE severity for those patients with multiple occurrences of the same event
- All TEAEs leading to permanent treatment discontinuation (and patient listing)

An AE patient listing will be provided for all patient deaths occurring during the respective TEAE periods (ie, double-blind or open-label) and the post-treatment period.

10.4.4.2. Other Safety

Definitions

The following definitions will be applied to laboratory parameters and vital signs:

- The potentially clinically significant value (PCSV) criteria are defined as abnormal values considered medically important by the sponsor according to predefined criteria/thresholds based on literature review and defined by the sponsor for clinical laboratory tests and vital signs. PCSV criteria will be provided in the SAP.
- PCSV criteria will determine which patients had at least 1 PCSV during the respective TEAE periods (double-blind or open-label), taking into account all evaluations performed during the respective TEAE periods, including unscheduled or repeated evaluations. The number of all such patients will be the numerator for the PCSV percentage.
- Double-blind treatment period: The treatment period used for quantitative analysis in the double-blind period is defined as the day after the first study drug administration to the day of the last double-blind study drug injection + 7 days for Group A. For Group B, the treatment period is defined from the day after the first administration of double-blind study treatment to the day of the last administration of double-blind study

treatment + 28 days for those patients not proceeding into the open-label treatment period, or up to the day of the first open-label study treatment administration for those patients proceeding into the open-label treatment period.

- Open-label treatment period: The treatment period used for quantitative analysis in the open-label study period is defined from the day after the first dose of open-label study treatment to the day of the last dose of open label study treatment + 28 days.

Analysis

Summary statistics of all laboratory variables (including lipid HDL-C) and all vital signs parameters (raw data and changes from baseline) will be calculated for each protocol scheduled visit assessed during the respective treatment periods. For selected parameters, mean changes from baseline with the corresponding standard error will be plotted over time (at same time points) in each treatment group.

The incidence of PCSVs at any time during the respective TEAE periods will be summarized regardless of the baseline level, and again according to the following baseline categories:

- Normal/missing
- Abnormal according to PCSA criterion or criteria

For laboratory parameters for which PCSA criterion is not defined, similar table(s) using the normal range will be provided.

Listings will be provided with flags indicating the laboratory values meeting PCSV criteria.

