5.8. Analysis of Safety Data

In general, for the double-blind period, the summary of safety results for patients in the double-blind SAF population will be presented by route of administration (Group A or Group B) and pooling the evinacumab dose regimens within each route of administration (Group A or Group B), with the intent to maximize efforts to identify potential safety signals. The treatment group data (individual evinacumab dose regimens and placebo) will also be presented with the intent to support the pooled dose regimens. No formal inferential testing will be performed. Summaries will be descriptive in nature.

For Group B, summaries of safety results for the open-label period will be presented for patients in the open-label SAF, by the total number of patients administered open-label study treatment (i.e., 15 mg/kg IV), as well as by the patient subgroups of study treatment received in the DBTP (i.e., 5 mg/kg IV, 15 mg/kg IV, or placebo). Summaries will be descriptive in nature.

General common rules

All safety analyses will be performed, unless otherwise specified, using the following common rules:

- For DBTP, safety data in patients who do not belong to the double-blind safety analysis set (i.e., exposed but not randomized) will be listed separately.
- PCSV values are defined as abnormal values considered medically important by the Sponsor according to predefined criteria/thresholds based on literature review and defined by the Sponsor for clinical laboratory tests and vital signs (PCSV version dated January 2009 [[Appendix 10.4](#)]). Considering that the threshold defined in the PCSV list for monocytes and basophils can be below the ULN, the following PCSV criterion will be used for the PCSV analysis of monocytes and basophils:
 - PCSV criterion for monocytes: >0.7 Giga/L or $>ULN$ (if $ULN \geq 0.7$ Giga/L).
 - PCSV criterion for basophils: >0.1 Giga/L or $>ULN$ (if $ULN \geq 0.1$ Giga/L).
- PCSV criteria will determine which patients had at least 1 PCSV during the respective TEAE periods, taking into account all evaluations including unscheduled or repeated evaluations.
- The treatment-emergent PCSV denominator by treatment group for a given parameter will be based on the number of patients assessed for that given parameter at least once during the respective TEAE periods.

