5.8.3. Clinical Laboratory Measurements

The following definitions will be applied to laboratory parameters:

- Double-blind treatment period: The treatment period used for quantitative analysis in the double-blind period is defined as the day after the first study drug administration to the day of the last double-blind study drug injection + 7 days for Group A. For Group B, the treatment period is defined from the day after the first administration of double-blind study treatment to the day of the last administration of double-blind study treatment + 28 days for those patients not proceeding into the open-label treatment period, or up to the day of the first open-label study treatment administration for those patients proceeding into the open-label treatment period.
- Open-label treatment period: The treatment period used for quantitative analysis in the open-label study period is defined from the day after the first dose of open-label study treatment to the day of the last dose of open label study treatment + 28 days.

For respective treatment period (DBTP and OLTP), clinical laboratory parameter actual values (quantitative) and change from baseline values will be descriptively summarized at baseline and each post-baseline visit by at least patient number, mean, median, Q1, Q3, SD, minimum and maximum. Clinical laboratory parameters mean changes from baseline, with the corresponding SE, can be plotted at each visit in the case results warrant further investigation. These parameters will be presented by the biological functions defined in Section 4.8.2. For glucose, only fasting samples will be included in the summaries.

Individual patient laboratory parameter measurements will be additionally evaluated by PCSV criteria (See Appendix 10.4), specifically identifying patients with at least one post-baseline measurement that meets the PCSV criteria within the respective TEAE periods. These laboratory parameters will be presented by the biological functions defined in Section 4.8.2. The incidence of PCSVs at any time during the respective TEAE periods will be summarized regardless of the baseline level, and again according to the following baseline categories:

- Normal (according to PCSV criterion/criteria)/missing
- Abnormal according to PCSV criterion or criteria

Patient listings of laboratory measurements that meet PCSV criteria will be provided for the report appendix. For those laboratory parameters that don't have an associated PCSV criteria,

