10.4. Criteria for Potentially Clinically Significant Values (PCSV)

Parameter	PCSV
Clinical chemistry	
ALT	By distribution analysis: >2 ULN and baseline \leq 2 ULN >3 ULN and baseline \leq 3 ULN >5 ULN and baseline \leq 5 ULN >10 ULN and baseline \leq 10 ULN >20 ULN and baseline \leq 20 ULN
AST	By distribution analysis: >2 ULN and baseline \leq 2 ULN >3 ULN and baseline \leq 3 ULN >5 ULN and baseline \leq 5 ULN >10 ULN and baseline \leq 10 ULN >20 ULN and baseline \leq 20 ULN
Alkaline Phosphatase	> 1.5 ULN and baseline \leq 1.5 ULN
Total Bilirubin	> 1.5 ULN and baseline \leq 1.5 ULN > 2 ULN and baseline \leq 2 ULN
Conjugated bilirubin	> 35% total bilirubin (when total bilirubin >1.5 ULN)
ALT and Total Bilirubin	ALT > 3 ULN and Total Bilirubin > 2 ULN and baseline ALT \leq 3 ULN or Total bilirubin \leq 2 ULN
CPK	> 3 ULN and \leq 5 ULN and baseline \leq 3ULN >5 ULN and \leq 10 ULN and baseline \leq 5 ULN >10 ULN and baseline \leq 10 ULN
Creatinine	\geq 150 μ mol/L (adults) \geq 30% from baseline \geq 100% from baseline
CLcr (mL/min) (Estimated creatinine clearance based on the Cockcroft-Gault equation)	\geq 15 - <30 (severe decrease in GFR) \geq 30 - < 60 (moderate decrease in GFR) \geq 60 - <90 (mild decrease in GFR) \geq 90 (normal GFR)
eGFR (mL/min/1.73m ²) (Estimate of GFR based on an MDRD equation)	\geq 15 - <30 (severe decrease in GFR) \geq 30 - < 60 (moderate decrease in GFR) \geq 60 - <90 (mild decrease in GFR) \geq 90 (normal GFR)

Parameter	PCSV
Uric Acid Hyperuricemia: Hypouricemia:	>408 µmol/L <120 µmol/L
Blood Urea Nitrogen	≥17 mmol/L
Chloride	<80 mmol/L >115 mmol/L
Sodium	≤129 mmol/L ≥ 160 mmol/L
Potassium	< 3 mmol/L ≥ 5.5 mmol/L
Glucose Hypoglycaemia Hyperglycaemia	≤ 3.9 mmol/L and < LLN ≥ 7 mmol/L (fasted); ≥ 11.1 mmol/L (unfasted)
HbA1c	>8%
Albumin	≤25 g/L
CRP	> 2 ULN or >10 mg/L, if ULN not provided
Hematology	
WBC	< 3.0 Giga/L (3000/ mm ³) (Non-Black) < 2.0 Giga/L (2000/ mm ³) (Black) ≥16.0 Giga/L (16000/ mm ³)
Lymphocytes	>4.0 Giga/L
Neutrophils	< 1.5 Giga/L (1500/ mm ³) (Non-Black) < 1.0 Giga/L (1000/ mm ³) (Black)
Monocytes	>0.7 Giga/L
Eosinophils	> 0.5 Giga/L (500/ mm ³) or > ULN if ULN ≥ 0.5 Giga/L
Hemoglobin	≤115 g/L (Male); ≤95 g/L (Female) ≥185 g/L (Male); ≥165 g/L (Female) Decrease from Baseline ≥15 g/L Decrease from Baseline ≥20 g/L
Hematocrit	≤0.37 v/v (Male) ; ≤0.32 v/v (Female) ≥0.55 v/v (Male) ; ≥0.5 v/v (Female)
RBC	≥6 Tera/L

Parameter	PCSV
Platelets	< 100 Giga/L (100 000/mm ³) ≥700 Giga/L (700000/mm ³)
Urinalysis	

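### Each liver and CPK PCSV tier requires a baseline at or below its own cutoff, so the planned all-baselines count leaves out patients above it and the abnormal-baseline row, classed by that tier, is empty

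*Protocol*

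**What the plan says.** Protocol 10.4.4.2 leaves the definitions to the SAP ("PCSV criteria will be provided in the SAP") and fixes the form of the summary: "The incidence of PCSVs at any time during the respective TEAE periods will be summarized regardless of the baseline level", followed by a split into two baseline categories. The second category is "Abnormal according to PCSA criterion or criteria". SAP 5.8.3 keeps the same three summaries and labels the rows "Normal (according to PCSV criterion/criteria)/missing" and "Abnormal according to PCSV criterion or criteria".

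SAP 10.4 supplies the criteria. The ALT entry opens "By distribution analysis: >2 ULN and baseline" and continues with the same 2 x ULN limit on the baseline. The same construction is used throughout:

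- ALT and AST: cutoffs at 2, 3, 5, 10 and 20 x ULN.
- Alkaline phosphatase: one cutoff, 1.5 x ULN.
- Total bilirubin: cutoffs at 1.5 and 2 x ULN.
- CPK: bands starting at 3, 5 and 10 x ULN.

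Each tier requires a baseline no higher than its own cutoff (for CPK, the lower limit of the band).

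SAP 5.8 sets the denominator, by treatment group and parameter, as "based on the number of patients assessed for that given parameter at least once during the respective TEAE periods". It is not limited to patients whose baseline allows them to meet the criterion.

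**The concern.** The summary and the definition do not fit together. The summary promises a count that ignores baseline and a separate row for patients who start abnormal. The definition has already removed those patients, tier by tier. A reader of the finished tables would take the first count as covering everyone, and would take a zero in the abnormal row as an observation when it follows from the definition.

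At stake is the reading of the hepatic and muscle laboratory tables. The listings of values meeting PCSV criteria (SAP 5.8.3) and the PCSV parts of the hepatic and muscle AESI derivations (SAP 10.3) inherit the same condition. Efficacy analyses are not touched.

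**Working it through.** The plan gives no figure to reproduce, so the check is one of logic, followed by examples.

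**Step 1: one tier.** Let k be the cutoff, B the baseline and Y a post-baseline value, in multiples of ULN. The criterion is Y > k and B ≤ k (for CPK, Y also stays within the band).

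- All-baselines numerator: Y > k and B ≤ k.
- Normal/missing row, classed by k: the same patients. SAP 6.3 puts missing baselines in this row.
- Abnormal row, classed by k: Y > k and B ≤ k and B > k, which is impossible, so 0.

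All pairs (B, Y) from 0.1 to 40 x ULN in steps of 0.1 were enumerated. No flagged pair had a baseline above the tier in any of the 11 distinct tiers (ALT/AST 5, alkaline phosphatase 1, bilirubin 2, CPK 3).

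**Step 2: across tiers.**

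| Parameter | Counted (tier met) | Not counted at any tier |
|---|---|---|
| ALT/AST | 1.5 to 2.5 (>2); 2.5 to 3.5 (>3) | 2.1 to 2.9; 6 to 9.9; 21 to 40 |
| Alkaline phosphatase | 1.2 to 1.6 (>1.5) | 1.6 to 5 |
| Total bilirubin | 1.6 to 2.5 (>2) | 2.1 to 6 |
| CPK | 4 to 6 (>5); 5.5 to 12 (>10) | 3.5 to 4.9; 11 to 40 |

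The loss is confined to rises within a tier and rises from above the top tier. For alkaline phosphatase, which has one tier, it covers every baseline above 1.5 x ULN.

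**Step 3: who can be above a cutoff at baseline.** Protocol 6.2.3 excludes ALT or AST above 2 x ULN and CPK above 3 x ULN at screening. These are the lowest tiers. Randomization labs are not used for that exclusion, so a day 1 baseline can still exceed them. The laboratory exclusions set no limit for alkaline phosphatase or bilirubin.

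**Step 4: size, as an illustration only.** The documents do not give the share p of patients above a cutoff at baseline. Assume p between 1% and 5%.

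- Group A, 144 patients: 144 × 0.01 = 1.4 to 144 × 0.05 = 7.2.
- Group B, 108 patients: 108 × 0.01 = 1.1 to 108 × 0.05 = 5.4.
- Both groups, 252 patients: 2.5 to 12.6.

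These are patients who cannot enter that tier's numerator, not missed events. If x of n assessed patients meet the criterion, the table shows x/n, whereas the proportion among those able to meet it is x/[n(1 − p)]. The reported figure is (1 − p) times that: 0.99 at 1%, 0.95 at 5%.

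**The case against.** The best defence is that the baseline clause is deliberate. SAP 5.8 describes the PCSV denominator as treatment-emergent, and a clause of this kind is one ordinary way to define emergence. The three-way summary is a general rule. It works for parameters without such a clause, for example potassium, albumin and HbA1c, and is merely redundant for the liver tests and CPK. Removing the clause outright would count a stable alkaline phosphatase of 1.6 x ULN, or a bilirubin falling from 3 to 1.6 x ULN, as an event. This part stands and shapes the fix. It does not rescue a table labelled as ignoring baseline when it does not, or a denominator that includes patients who cannot meet the criterion.

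Second, the abnormal row need not be classed tier by tier. The SAP refers to criterion or criteria without saying which. If a patient is classed once per parameter by the lowest tier, the row can fill at higher tiers and is empty only for alkaline phosphatase and at the lowest tier of the others. That also stands, although the choice is then left to the programmer. The all-baselines count for each tier still omits patients above that tier.

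Third, other outputs show some of these patients. The eDISH plot and the Hy's law listing (SAP 5.8.3) have no baseline condition. The conjugated bilirubin row has none either. The combined ALT/bilirubin criterion joins its two baseline conditions with an or, so a raised bilirubin with ALT at or below 3 x ULN at baseline can still qualify. The SMQs, the musculoskeletal terms and the by-visit values and changes add more. Protocol 9.4.3 requires AESI reporting of ALT or AST at twice baseline when baseline is at or above ULN, though SAP 10.3 does not list that rule among its hepatic derivations. Cover is thinnest for alkaline phosphatase, where mainly the by-visit summaries and reported adverse events remain.

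**Conclusion.** The inconsistency is real and minor. For each ALT, AST, alkaline phosphatase, total bilirubin and CPK tier, the all-baselines count is the count among patients with baseline at or below the cutoff (or missing). The abnormal row is empty when baseline is classed by that tier, and patients above the cutoff stay in the denominator. This follows from the text alone.

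A reader might infer more, and three such inferences fail:

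- The criteria do not require a normal baseline. The limit is the tier's own cutoff, from 1.5 to 20 x ULN.
- Worsening from a raised baseline is not always lost, since crossing a higher tier is counted.
- Hepatic or muscle signals in such patients would not vanish from the report, given the other outputs.

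Nor can the overall incidence be called understated without deciding whether pre-existing elevations should count.

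The number affected cannot be derived from the documents. It is probably small, and smallest for ALT, AST and CPK because of the screening limits. Any percentage, including the 1% to 5% used above, is an assumption. The cases that matter most are alkaline phosphatase above 1.5 x ULN and total bilirubin above 2 x ULN at baseline.

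**What to change.** In SAP 10.4 and 5.8.3, for ALT, AST, alkaline phosphatase, total bilirubin and CPK:

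(a) Keep the current criterion as a separately labelled treatment-emergent count. Restrict its denominator to patients assessed whose baseline is at or below the tier or missing.

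(b) For the all-baselines count, use the threshold alone (for CPK, the band limits), with all assessed patients in the denominator.

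(c) For the abnormal-baseline row, class baseline by the threshold alone, and count post-baseline values that exceed both the threshold and the patient's own baseline.

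The cost is appendix wording and slightly more table programming. Pooled counts under (b) will be slightly higher and will include pre-existing elevations. For that reason (a) should sit beside (b), so that stable or improving values are not read as new events. No data collection changes.
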